### **Minimization of risks**

**Suicide.** As part of baseline assessment potential participants will be assessed using the PHQ-9, which includes an item on suicidality. Those who assent to this item will complete the P4 screening tool for active suicide. Participants who do not assent to this item will not complete the P4 screening tool (93). Using this method, those who fall in the category of more than minimal risk will undergo comprehensive assessment for suicidal risk. This will comprise an assessment by the research mental health nurse (RMN). Participants confirmed at risk for suicide attempt will be referred immediately to psychiatric services and not enrolled. The research team will follow up to ensure that the patient has reached services. An electronic record will be kept of all the referrals and will be updated as follow up information is made available. This risk protocol will be adhered to for participants who are enrolled and who indicate suicidal ideation at any point during their study participation. All members of the research team will be trained in this protocol with Standard Operating Procedure (SOP) available for reference.

**Treatment procedures.** The design of the current study provides for active treatment for depression in the experimental condition, allows for enhanced usual care for depression based on WHO guidelines in the control arm, and monitoring of symptoms in both conditions. The interventions will be implemented by Shona-speaking adherence counsellors who will be trained in the study protocol. Treatment fidelity procedures will help ensure that clinical protocols are being implemented as designed. Study interventionists will receive specific training to address distress related to depression operationalized for people also managing HIV. All adherence counsellors will also receive training in WHO mhGAP Guidelines for managing depression.

Higher than usual levels of distress. Additional procedures will be in place to further protect participants who may experience higher than usual levels of distress, regardless of treatment

assignment. Adherence counsellors and assessors will be trained by the study Clinical Psychologist and psychiatrist to be vigilant and sensitive to signs of distress in our participants. For those in the treatment condition, the counsellor will re-administer the screening scale for depression at session 6. the stepped-care model ensures that if the score remains above cut-off the counsellor will refer to a nurse with the view of prescribing an antidepressant.

The exclusion criterion prohibiting participants with serious untreated mental illness from participating in the study ensures that those who would be most likely to experience this high level of distress in response to the study procedures are not enrolled.

**Increases in depression.** For participants in the control condition, if there are increases in depression at study visits, the usual care adherence counsellor will have the option to make appropriate referrals for next-level of care. A trained Community Psychiatric Nurse is available to see patients as part of routine care at Marondera Provincial Hospital, which is one of the study sites. Those in the control condition in whom the adherence counselor or wider treatment team consider needs next-level care have the option of referral to the Community Psychiatric Nurse at Marondera Provincial Hospital or referral to the psychiatric clinic at Chitungwiza Central Hospital. In addition, the site PI and the study Research Mental Health Nurse will either be on-site or on-call and contactable by cell phone. They will provide supervision and additional counselling if required. In the event that inpatient level of care is required it is available at Marondera Provincial Hospital and Chitungwiza Central hospital. In the event that study participants need more than this level of care, transport will be arranged for them to the Tertiary Hospital in the capital by ambulance.

Participants in the intervention arm will have ready access to adherence counsellors and the Research Nurses and the Zimbabwe Programme Manager (who will be on-site much of the time) all of whom are available by cell phone 24 hours a day, 7 days a week. Study procedures do not preclude participant referral for additional care and treatment and in each case, where additional levels of care are required, decisions regarding the participant's continuation in the study will be based solely on a consideration of the participant's welfare.

**Blood extraction.** With respect to blood extraction, this procedure will be carried out by a trained research assistant or nurses to minimize the accidental injury or discomfort to the participants. Participants who experience harm as a result of this procedure will receive first aid from study staff and referral to medical professional if needed.

**Summary of minimization of risks.** To emphasize, in the case of treatment non-response or other deterioration or relapse, the adherence counsellors, study nurses, psychologist or assessors will refer patients to appropriate clinical care. Participants who begin treatment and experience adverse outcomes sufficient to require removal from the study will also receive linkage to an appropriate level of clinical care. The exact nature of "appropriate clinical care" will be determined by the judgment of clinicians familiar with the specific participant and may include psychotherapy referrals, arrangements for evaluation in a local Emergency Department, or referrals to hospital outpatient or inpatient levels of care.

For participants who consent to have medical information released from their medical records this information will be restricted to specific medical information related to their HIV disease status and its treatment (current and previous ART regimen, date of treatment initiation, CD4 cell number and HIV viral load during the course of the study), missed HIV care appointments, and concomitant treatment for mood disorders (psychopharmacological or psychotherapeutic, date of initiation of treatment). As both patients with either HIV or mental health problems in

Zimbabwe may experience stigma related to these issues, this information will be safeguarded under the same procedures identified above (Section 27 and 29). Medical record information will be obtained either in person by study personnel or through secure file transfer.

### **Expected benefits**

Although it is possible that there will be no direct benefit to participants in this study, those who participate in this study may benefit from the close monitoring of mood and adherence. Those assigned to the treatment condition may benefit from the intervention provided to treat their depression and support improvements in their ART medication adherence and viral suppression. These potential benefits are provided without charge. Information provided as part of the active and enhanced usual care interventions may help participants better understand their ART enabling them to take it more effectively, and better understand their mood disorder and maintain improvement over the long-term.

Participants in the control condition will have the opportunity to receive the stepped care-AD intervention after 12 months, free of charge. All participants are also provided with a small amount of financial remuneration for completing their participation. We hypothesize that the active treatment will be associated with beneficial effects for both depression and medication adherence and it is anticipated that some of our study participants may reap these benefits.

### **Participant remuneration**

Reimbursement will be given to participants in line with local standards for providing a brief amount of data for clinical session visits. The stepped care-AD intervention arm participants will be asked to attend six clinical sessions, plus a booster session as part of the research study. The EUC control arm participants will be asked to attend two clinical sessions as part of the research study. Although those in the EUC arm will have fewer scheduled clinical sessions, the same total amount will be provided to participants attending all clinical sessions and research assessments in both arms. Table 2 shows the participant reimbursement scheme.

**Table 2: Participant Reimbursement Scheme**

	Control Arm	Intervention Arm
Baseline Session	1 session @ \$6	1 session @ \$6
Research Assessment	3 sessions @ \$8	3 sessions @ \$4
Clinical Session	2 sessions @ \$8	6 sessions @ \$4
Booster Clinical Session		1 session @ \$4
Total	6 sessions @ \$46	9 sessions @ \$46

The payment arrangement will be managed through the trial by the research assistants and University of Zimbabwe Programme Manager to maintain blinding. This will mean the independent assessors will not be involved in participant reimbursement and therefore are unable to be unblinded by knowledge of reimbursement amount. To reduce attrition, participants will be paid for completing the 4, 8, and 12-month final study assessment (12-month post randomization), as well as for the full baseline assessment. Participant payment is not contingent upon improvement or any other study data at the time of assessment or follow-up.

### **31a. Dissemination policy**

Figure 4 illustrates our approximate expected study timeline for the 5-year study.

	01/07/18	01/07/19	01/07/20	01/07/21	01/07/22	01/07/23
Study Start up/ IRB/ Hire & Train Staff						
Finalize all study SOPs						
Enroll and Randomize 290 Participants						
Active Treatment Phase						
12 month follow-up						
Data analyses & Economic Evaluation						
Dissemination of Project Results						

**Dissemination Policy.** Our aim to share our findings with scientists in the field, research participants and Zimbabweans who can influence local policy.

**Publishing manuscripts.** We plan to publish the findings of this study in peer-reviewed journals. Specifically, our current goals are to publish: (1) a main outcome paper in a journal such as JAMA Psychiatry this paper may also include health economics; (2) a manuscript about our protocol in a publication such as a BMC open access journal; (3) a baseline paper on the correlates of depression and mental health in a journal such as AIDS and Behavior; (4) a paper examining the relationship between depression, treatment adherence, and viral load in a journal such as JCCP or Health Psychology; and (5) a paper on adherence methods in a journal such as AIDS and Behavior or the IAPAC Journal. Manuscripts other than those listed may also be published.

**Research Participants:** Participants will be given written feedback on the results of the trial. In addition, participants will be invited to dissemination workshops where results of the trial will be verbally explained, and participants will be invited to ask questions. Participants will also be signposted to how they can access study publications.

**Scientific Conferences.** We plan to present findings from this study at several scientific conferences during year 4 of the project and a year after the project is set to end. At the moment, we plan to present our findings at the IAPAC Conference in Miami, Florida, the IAS Conference on HIV Science and at CROI. Additionally, we also plan to look into presenting our findings at a global mental health conference.

**Local stakeholders meeting.** We plan to disseminate our results to people in Zimbabwe who may directly benefit from our findings. Specifically, we plan to present our findings at stakeholder meetings in years 4 and 5 of the project. Attendees at these meetings will include Ministry of Health officials, providers and workers at clinics, service users and advocates. Additionally, we also plan to present our findings at community advisory boards.

**ClinicalTrials.gov.** We will ensure that the study is registered on ClinicalTrials.gov, that the results information is submitted to ClinicalTrials.gov as outlined in the policy and according to

the specific timelines stated in the policy, and that all registration information and results information is up to date. Specifically, the study will be registered on ClinicalTrials.gov before the first subject is enrolled and will be updated once every 12 months at the very minimum. Summary results will also be reported less than a year after trial completion. All ClinicalTrials.gov responsibilities will be managed by [name] and study staff at King's College London, the study's coordinating site. In addition, all informed consent documents in this study will include a specific statement relating to the posting of clinical trials information on ClinicalTrials.gov. Please note that since this study does not evaluate at least one drug, biological, or device product regulated by the United States Food and Drug Administration, it is not an Applicable Clinical Trial (ACT). Therefore, it is subject to the NIH Policy on Dissemination of NIH Funded Clinical Trial Information, but not FDAAA 801 as implemented by 42 CFR Part 11 (the Final Rule). King's College London policy (KHP-CTO SOP 12 'Application and Maintenance of a CTA') details the legislative requirement for publication in line with NIH policy, which states the study results will be reported no later than 12 months from end of trial declaration.

31b. The principal investigators, and other investigators involved with this project, will be involved in paper authorship. There are no plans to use professional writers.

31c. We plan to make an annotated dataset available to scientists working in the field who want to do secondary data analysis. We will make this dataset available once the parent research team (including researchers in the United Kingdom, United States, and Zimbabwe) has finished their planned primary and secondary analyses.

23/03/2022	V1.02	TENDAI protocol Version 10.0 2022 (2)	
Updates to status of trial personnel
 
Some correction of typos, redundancies and minor clarifications throughout
 
Addition of a second recruitment site, Sections 1.2, 1.4, 2.2, 3.1
 
COVID-19 measures have been added, Section 1.8.1, 5
 
Clarification of blinding status of senior statistician, Section 3.1
 
Clarify will fit two binary viral suppression models one without baseline viral load (providing marginal estimate), one with (providing conditional estimate), Section 3.1, 3.1.1
 
Add consideration of random slopes for mixed models, setting of undetectable viral loads, and clarification of presentation of results from logistic mixed and GEE models, Section 3.1.2
 
Clarify predictors in moderation models and that time will not be included for PHQ-9/will be average effect over course of follow-up, Section 3.1.3
 
Clarify adherence variable assessed to predict missing data is self-report adherence, Section 3.1.4.5
 
Clarify variables for imputation model and correct process for incorporating moderating variable in imputation model, Section 3.1.4.5
 
Clarify that per protocol analysis will only be done for primary outcome binary viral suppression, Section 3.1.4.7
 
Clarification and change to viral load assumption for deaths sensitivity analyses, Section 3.1.5.1
 
Addition of COVID-19-related data summaries and sensitivity analyses, Section 3.1.5.2
 
Software – update to Stata versions

			Replaced Appendix 1 Scoring with reference to up to date Codebook document with scoring
05/08/2022	V1.03	TENDAI protocol Version 11.0 Mar 2022	
Comments added resolving queries to and by the team.
 
Dates when COVID measures were added and a date for when the pandemic started to allow for analyses described in Section 3.1.5.2.
 
Coding of occupations into an occupational class variable to be summarised at baseline, see Section 2.2

22/08/2022	V2.0	TENDAI protocol Version 11.0 Mar 2022	Create V2.0 signed by DSMB Chair

Amendments to SAP after signoff of version 1.0	2
QUANTITATIVE ANALYSIS PLAN	5
Contents.....	7
1. Description of the trial	7
1.1 Principal research objectives to be addressed	7
1.2 Trial design including blinding.....	8
Figure 1. Trial design flow diagram.....	9
1.3 Eligibility screening	10
1.3.1 Inclusion criteria	10
1.3.2 Exclusion criteria	10
1.4 Method of allocation of groups.....	10

(On sabbatical doing a fellowship 2020-2021 with some continued involvement, interim cover by lead clinical psychologist and research associate)

Previous Trial statistician (left KCL)
[name]

Trial statistician
TBD
Institute of Psychiatry, Psychology and Neuroscience
King's College London, [name]
[name]
Tel: TBD

Database Manager
[name], LCSW
Behavioral Medicine Program, Department of Psychiatry
Massachusetts General Hospital
[name]
[name]
[contact]

TENDAI Statistical Analysis Plan

Lead Clinical Psychologist

[name]

Faculty of Medicine and Health Sciences

Research Support Centre

[name] Zimbabwe

Research Associate

[name]

Faculty of Medicine and Health Sciences

Research Support Centre

[name] Zimbabwe

Contents

This document contains up to date statistical analysis plans (with version numbers and dates) including a quantitative analysis plan and a schedule of assessments and measures.

This SAP refers solely to the main analysis of the primary and secondary trial outcomes, i.e. the analysis to be performed in producing the main trial results paper. It mentions health economic, mediator, and other variables that have been measured, but does not describe these analyses associated with these variables. The health economic analysis will be described in a separate analysis plan. Any qualitative or mediation analysis plans will be dealt with in separate analysis plans.

1. Description of the trial

Problem Solving Therapy (PST), which is an evidence-based psychological and behavioural intervention for depression and an ingredient of CBT, has been previously been tested in a low-income country setting in treatment for depression, also for depression following gender-based violence and depression in post-conflict settings (Chibanda et al, Rahman et al). In Zimbabwe the study team has embedded PST into an intervention, stepped care for adherence (stepped care-AD). This form of PST combined with a culturally-adapted version of Life-Steps (a CBT and problem-solving methodology for improving adherence, viral suppression and depression) has been combined into a new intervention TENDAI (meaning 'thankful' in the Shona language). This has been tested in a feasibility trial in Zimbabwe (Nyamayaro et al, [name] et al). This trial aims to determine whether the TENDAI intervention is effective in a real-world setting.

The trial will recruit HIV positive, not virally suppressed patients who are able to provide informed consent, who have been taking anti-retroviral treatment (ART) for at least 6 months, who are clinically depressed and, where prescribed anti-depressants, have been on a stable regimen for at least 2 months. Those participants will be randomised 1:1 into enhanced usual care (EUC) or Stepped Care-AD (TENDAI). Please refer to the protocol v11.0 04 March 2022 for more detail.

1.1 Principal research objectives to be addressed

Primary objectives

To evaluate the effectiveness of the task-shifted stepped care-AD intervention on viral suppression compared with Enhanced Usual Care (EUC) at 12-months post-randomisation follow-up.

Secondary objectives

To investigate the effectiveness of the TENDAI intervention compared with Enhanced Usual Care (EUC):

1. on depression at 12 months post-randomisation (PHQ-9),
2. on adherence at 4, 8 and 12 months post-randomisation defined as the proportion achieving at least 90% adherence assessed through pharmacy refill,
3. on adherence at 4, 8 and 12 months post-randomisation through self-report,
4. on viral load (mean log viral load of viral copies per mL) at 12 months post-randomisation.

Tertiary objectives

1. To estimate the cost effectiveness of the TENDAI intervention on viral suppression and quality of life at 12-months (using the CSRI and EQ-5D-3L (Shona dialect version)). This tertiary objective will be addressed in a separate Health Economic Analysis Plan.

Exploratory Objectives

Additionally, we intend to investigate mediation and moderation hypotheses.

Mediation: we intend to investigate whether: a) the effect of TENDAI on the depression and adherence outcomes are mediated by improvements in social support, Adherence Self-efficacy scale (ASES) or Problem Solving Skills subscale (PSSS), b) the effect of TENDAI on viral suppression is mediated by depression or adherence. For (b) we will initially explore each of self-report, pharmacy refill, and DBS measures of adherence as separate potential mediators, then also a composite measure of adherence using all three as indicators of an adherence latent variable. As this SAP refers only to the analysis for the main trial paper, we will not describe the mediation analysis further in this document.

[figure not shown]
Moderation: we intend to investigate whether the effect of TENDAI vs EUC differs by sex, on the primary outcome of viral suppression, and the secondary outcomes of self-report adherence, and depression, see Sections 1.8.5 and 3.1.3. Other more exploratory moderation hypotheses may be published in another paper.

1.2 Trial design including blinding

A 12-month parallel arm randomised controlled trial of the TENDAI intervention on depression and ART adherence in adult patients living with HIV compared with enhanced usual care (EUC). Participants will be randomised 1:1 to 12-months treatment with either TENDAI or EUC. Randomisation, which will be stratified by site as the study will now take place in the Chitungwiza Central Hospital as well as the Marondera Provincial Hospital, will be conducted using a variable block randomisation schema (using Sealed Envelope) coordinated through the trial REDCap database. Only the Zimbabwean site Project Manager and the trial Database Manager have the ability to randomise participants. Eligibility for randomisation is confirmed on a weekly cross-site call, which involves the Zimbabwe study team, the study Principal Investigators, and study Clinical supervisors. The principal investigators, local and London programme managers, data manager and interventionists are unblinded. Blinded independent assessors will administer the PHQ-9, EQ-5D-3L, self-report adherence questionnaires at follow-up. The senior statistician will be fully blinded, and the junior statistician will be unblinded.

Figure 1. Trial design flow diagram

Schematic diagram of flow of participants (potential and actual) through the pre-trial assessment and trial. Please see the CONSORT diagram (Figure 2) for detail on how this will be reported.

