**5d. Committees - General approach and meeting schedule:** An organizational system for this study that is well-coordinated from a data management schedule has been developed. The overarching context for the data monitoring and management procedures is to maintain active, clear communication at each site and between sites. Specifically, Drs. [name], [name], and [name] will hold weekly video meetings (via a service such as Skype, WebEx, or Zoom) with the site study staff including the Zimbabwe-based Programme Manager and the London based Project Manager, to direct study activities. This meeting schedule will be maintained throughout all years of the project. These meetings will address consistency of procedures, problems/challenges, and general training issues. For example, issues of data collection, budget, recruitment, data management and analysis will be addressed, training will be performed, and the protocol and assessment procedures will be reviewed on an ongoing basis. Agenda items that may involve the revealing of randomization condition will take place towards the end of the meeting, after study staff who are required to remain blinded (chiefly the Study Statisticians) have left. Any human subjects issues related to the ongoing work will also be discussed. In addition, the local Clinical Psychologist and the Research Coordinator will be involved in weekly supervision of adherence counsellors. These meetings will focus on supervision of intervention and assessment procedures. The London-based Programme Manager and MGH data manager will generate data related quality control reports—which will include information about data uploads from study tablets, issues with visit data that require follow-up and/or correction, and data corrections that have been made—to feed back to the sites to make any corrections in as close to real time as possible.

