### Data Validation

Each month, a random subset of visits from the previous month (20%, or the closest whole number) will be assessed for data quality and accuracy (missing data, discrepancies in responses between questionnaires, data that is out of range). These checks will be documented using the Data Review and Correction form in the Project Management Database on REDCap. Quality assurance checks will be assigned to Research Assistants by the Data Manager or the University of Zimbabwe Project Director. The Data Manager will ensure that the staff member conducting the check was not involved in the collection of data for that visit. Quality assurance checks will be completed within 2 weeks of assignment. Higher order data checking will be done by the statisticians (e.g. data completeness checks and higher-level logic checks, etc.). Further information on data validation will be found in the TENDAI Trial Data Validation Plan.

**Centralized data repository (MGH Site).** The study PI at Massachusetts General Hospital has coordinated research initiatives over the past 5 years that utilize centralized data management from multiple study sites and have established procedures and technologies in place. [name] will oversee that aspect of the study and the MGH Data Manager will have the operational responsibility for data management as described previously. Specifically, the MGH team will develop a study specific data management protocol and standard operating procedures for the creation and testing of all study questionnaires, data collection, quality control, and data extraction. The MGH team will provide ongoing oversight of data management throughout the study, and will be responsible for generating reports and datasets for quality control and data analysis. The Data Management team will make data available to the study statisticians for data checking and final analysis. Data management reports will be made to the DSMB by the MGH team.

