3.1 Main analysis of treatment differences

The main statistical analyses will follow the intention to treat principle as much as possible. The senior statistician will remain fully blind until an initial draft of the primary analysis report is complete and needs to be checked. The trial

statistician will be unblinded. Group difference estimates between TENDAI and EUC and associated 95% confidence intervals will be reported from models appropriate to the measurement schedules and nature of the outcome in question, i.e. depending on whether the outcome is continuous or categorical. The models that will be used are outlined in the following sections. Where the outcome variable is recorded at baseline it will generally be included in the analysis model as a covariate unless stated otherwise. The significance level for the difference between TENDAI and EUC on the primary outcome will be 5% (two-sided). This significance level will also be used for the secondary outcomes, but the reader will be alerted regarding the impact of multiple testing.

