If there are post-randomisation variables that predict missing outcome data, we will impute a number of datasets equal to the percentage missing data in the primary viral load outcome (Dong and Peng) or 50 datasets (whichever is higher). As well as the relevant variables from Sections 3.1.1 and 3.1.2, the imputation model will include all baseline and post-randomisation variables we find to predict missing outcome data and the putative moderating variable sex, imputing the trial arms separately as recommended by Thomas et al when moderation analysis is planned. We will endeavour to construct the imputation models as described, but if not viable, we may need to consider a set of simpler imputation models (i.e. when imputing with interaction terms we may need to remove some other variables from the imputation model). Where MI is used, we will produce estimates from both the complete case and MI data and include both in the statistical report, with the latter being the main estimates reported in the primary publication. If there are no post-randomisation variables that predict missing outcome data, but there are baseline variables predictive of missing data, these will be included in the non-logistic primary and secondary outcome analysis models (i.e. PHQ-9, self-report adherence, log viral load).

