3.1.4.8 Model assumption checks

The linear regression and linear mixed effects models assume normally distributed outcomes; this will be checked when describing the data and if substantial departures from normality occur, transformations will be considered. Residuals will be plotted to check for normality and inspected for outliers.

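### The protocol expects the study statisticians to stay blinded, but the SAP unblinds one at no stated time and leaves a few rule-free choices, including the coding of missing primary outcomes, open to that person

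*SAP*

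**What the plan says.** Protocol 5d orders the weekly meetings so that items which might reveal allocation come last, "after study staff who are required to remain blinded (chiefly the Study Statisticians) have left". It makes no exception for a junior statistician and gives no end date.

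SAP 1.2 states: "The senior statistician will be fully blinded, and the junior statistician will be unblinded". SAP 3.1 says the same of the trial statistician, again without a time point, and adds: "The senior statistician will remain fully blind until an initial draft of the primary analysis report is complete and needs to be checked". The junior statistician and the trial statistician appear to be the same role.

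On who handles the data, Protocol 19 says: "Higher order data checking will be done by the statisticians". It also says: "The Data Management team will make data available to the study statisticians for data checking and final analysis". Neither sentence separates senior from junior.

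The SAP leaves some decisions to be made on the data. In 3.1.4.5, if the planned imputation model is not viable, "we may need to consider a set of simpler imputation models". In 3.1.4.8, "if substantial departures from normality occur, transformations will be considered". SAP 1.8.2 and 3.1.1 code some missing 12-month viral loads as not suppressed on the evidence of medical or death records. They do not say who reads those records or whether the reader knows the arm.

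**The concern.** SAP 1.2 lists the principal investigators, programme managers, data manager and interventionists as unblinded, and participants know which treatment they receive. The remaining protections are the blinded outcome assessors, the laboratory endpoint with its fixed cut-off, and whatever blinding applies to the analysis. If the person who prepares the data and fits the models knows the arms, every choice without a rule can be influenced by that knowledge, even unintentionally.

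The coding of missing viral loads matters most because it changes the primary outcome itself. The imputation model comes next: where multiple imputation is used, SAP 3.1.4.5 makes its estimates the main published ones.

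**Working it through.** No figure in the plan depends on this point, so the check is a comparison of texts, followed by an illustration of scale.

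**1. Blinding status.** Protocol 5d: statisticians, in the plural, are to remain blinded, with no end date. SAP 1.2 and 3.1: senior blinded until a draft primary report exists; trial (junior) statistician unblinded, no date. The documents disagree.

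**2. Who does the work before the draft.** Neither document says so directly. If the senior is blind until the draft needs checking, someone else writes it, and the only other statistician named is unblinded. This is an inference from SAP 3.1.

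**3. Which choices are open.**
- Random slope (SAP 3.1.2): decided by a likelihood ratio test. Bounded.
- Whether to impute (SAP 3.1, 3.1.4.5): 5% tests of predictors and a 10% missingness floor. Bounded.
- COVID periods (SAP 3.1.5.2): tied to outside events and used only in a sensitivity analysis. Largely bounded, though the cut points are not yet set.
- Transformation (SAP 3.1.4.8): no threshold. Open.
- Simplifying the imputation model (SAP 3.1.4.5): no order of steps. Open.
- Record-based coding of missing viral load (SAP 1.8.2, 3.1.1): no assessor, no masking. Open.

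**4. Scope of the coding rule.** SAP 3.1.1 applies it to participants who died. SAP 1.8.2 accepts medical records pointing to a high viral load as well as an AIDS-related death, so as worded it also reaches survivors. Both sensitivity analyses in SAP 3.1.5.1 cover only those who died. Under the wording of 1.8.2, a re-coded survivor is never tested.

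**5. Illustration of scale.** The plan's 290 participants with 20% attrition give 290/2 × 0.8 = 116 per arm. The counts below are assumed to be borderline. The test is z = (p1 − p2) / √[p(1 − p)(1/n1 + 1/n2)], with p the pooled proportion.
- 67/116 v 53/116: difference 0.1207, standard error 0.0656, z = 1.839, p = 0.066.
- Two EUC missing values coded not suppressed, 67/116 v 53/118: z = 1.965, p = 0.049.
- Three so coded, 67/116 v 53/119: z = 2.027, p = 0.043.

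An unadjusted logistic model, closer to the SAP's analysis, gives 0.067, 0.050 and 0.043. Fisher's exact test gives 0.0514 and 0.0505 for the two re-coded cases, so neither falls below 0.05.

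If the re-coded participants are deaths, SAP 3.1.5.1 responds as follows.
- Excluding them returns 53/116 and p = 0.066.
- Coding them as suppressed gives 55/118 (z = 1.707, p = 0.088) or 56/119 (z = 1.642, p = 0.10).

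**6. Transformation.** In simulated trials with no effect (gamma-shaped PHQ-9, mean 8, SD 4, 116 per arm, all assumed), taking the smallest p-value over raw, square-root and log scales raised a 5% test to about 6%. That is deliberate selection, which the SAP does not permit, and it omits the planned baseline adjustment and mixed model.

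**The case against.** The strongest reply is that the protocol sentence concerns a meeting agenda. Protocol 17a, on masking, covers only the independent assessors. The SAP is the more specific document, states each statistician's status openly, and was signed by the DSMB chair. Protocol 17b allows no between-arm comparison until the trial ends, and a blinded senior with an unblinded junior can be a deliberate arrangement. This explains how the difference may have arisen but does not remove it: Protocol 5d still describes the statisticians as required to stay blinded, and the SAP gives no date for the change. A blinded senior protects the analysis only if that person makes the judgement calls, and SAP 3.1 brings the senior in once a result has been drafted.

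A second reply is that some planned work identifies the arm: therapy completion in the TENDAI arm as a predictor of missingness (SAP 3.1.4.5), session counts (2.3.1), and the per-protocol exclusion (3.1.4.7). This stands. It would be wrong to say that nothing in the plan needs an unblinded statistician, or to ask for every choice to be locked before completion data are released: the imputation decision itself uses those data.

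A third reply is that SAP 3.1.5.1 already tests the coding of deaths in both directions, and that Protocol 18b does not expect mortality to be a significant source of attrition. This also stands for deaths. It does not cover survivors re-coded under SAP 1.8.2.

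**Conclusion.** The conflict between Protocol 5d and SAP 1.2 and 3.1 is explicit and needs reconciling. With it goes a limited exposure: record-based coding of missing primary outcomes, transformation, and simplification of the imputation model can be decided with the arm known. That the unblinded statistician makes these choices is inferred from SAP 3.1.

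A reader might go further and infer that the plan assigns data queries and all modelling choices to someone who knows the arms. The documents do not say this. Protocol 19 gives data checking to the statisticians jointly, SAP 3.1.1 does not say who reads the records, and most of the data-dependent steps have numeric or external triggers.

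A reader might also infer that the result could be tipped unseen. For deaths it could not, because the sensitivity analyses would show it. The p-values above assume a borderline result and re-coding in one arm only, and the 6% assumes deliberate selection. They show scale and are not estimates of bias. The point is worth settling before analysis, and it changes no sample size or power figure.

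**What to change.** 1. Reconcile Protocol 5d with SAP 1.2 and 3.1, and state in the SAP when the trial statistician is unblinded.
2. Before any by-arm outcome result is produced, have the blinded senior statistician decide and date, on pooled or arm-masked data and records: every record-based coding of a missing 12-month viral load, the COVID period cut points, and any transformation.
3. Align SAP 1.8.2 with 3.1.1, or extend the sensitivity analyses in 3.1.5.1 to every re-coded participant, survivors included.
4. Leave the steps that need arm or completion data until after that dated lock: the completion-based missingness test, the imputation decision that follows from it, and the per-protocol analysis. Run them by the SAP's stated rules, with any simplification of the imputation model following an order written down in advance.

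The cost is SAP wording, a masked extract from the data manager, and a short delay at analysis. No extra staff are needed.
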